### **2.2.2. Interim Analysis**

#### **2.2.2.1. Futility Analysis**

A non-binding futility analysis for OS will be implemented after observing 33% (170 events) of the total number of required 514 events. The study may be considered futile if the estimated hazard ratio (HR) from Cox proportional-hazard model is equal to or greater than 0.95. The probability of stopping under null hypothesis is approximately 62%, and the probability of stopping under alternative hypothesis is approximately 10%.

After the futility analysis at 33% of the total number of OS events, on 26 June 2017, the IDMC requested a futility analysis once again at 45% of the total number of OS events. So, a non-binding futility analysis for OS will also be implemented after observing 45% (232 events) of the total number of required 514 OS events. The study may be considered futile if the estimated hazard ratio (HR) from Cox proportional-hazard model is equal to or greater than 0.93. The probability of stopping under null hypothesis is approximately 71%, and the probability of stopping under alternative hypothesis is approximately 9%.

YONDELIS®: Statistical Analysis Plan Study ET743-OVC-3006

### 2.2.2.2. *Interim Analysis*

One interim analysis is planned for this study after observing 60% (308 events) of the total number of required (514) events. The alpha spend will be 0.008 for the interim analysis. The exact timing of the interim analysis will be determined according to the planned number of events. The O'Brien-Fleming boundaries, as implemented by Lan-DeMets alpha spending function will be used for the efficacy boundary. Operating characteristics for these boundaries are presented in the following table.

Variable	Analyses	
	Interim	Final
Projected Observed OS Events	308	514
Anticipated Time to Analysis (months)	43	64
Anticipated Enrollment (n)	563	669
Efficacy Boundary (HR)	0.74	0.84
Boundary Crossing Prob. ( $H_0$ )	0.008	0.048
Cumulative $\alpha$ spent	0.008	0.050

HR=Hazard ratio;  $H_0$  = 0% improvement;  $H_1$  = 28% improvement

An Independent Data Monitoring Committee consisting of external members including clinicians and statistician will be formed. The committee will conduct periodic reviews of the safety data and will review the efficacy data according to the prescribed statistical plan.

Following the review of the study data for the second utility analysis by the IDMC on 15 December 2017, the HR for OS was 0.962, crossing the previously agreed upon threshold for futility of 0.93. In view of this result and the observed and expected higher toxicity in Arm A as compared with Arm B, the IDMC recommended discontinuing the study. The planned interim analysis will not be performed.

### 2.2.3. **Demographics and Baseline Characteristics**

Demographics and baseline characteristics will be summarized for all randomized subjects.

Age, weight, height, and body surface area (BSA) recorded on the CRF will be summarized descriptively. Age is calculated based on the date of birth at the time date of randomization. Baseline body mass index (BMI) will be calculated, using the formula:

$$\text{BMI} = \text{weight (kg)} / \text{length (m}^2\text{)}.$$

YONDELIS®: Statistical Analysis Plan Study ET743-OVC-3006

The BMI will be summarized, and the frequency counts of the different categories (<20, 20-<25, 25-<30, ≥30) will be displayed.

Age category (<65, ≥65), and race will be summarized with frequency counts.

For the ovarian cancer history, the histology and histological grade will be summarized. Time from initial diagnosis to the randomization, time from progression/recurrence during/after initial chemotherapy regimen to randomization, and time from end of first platinum-containing therapeutic line to disease progression will be calculated in months and summarized descriptively. Incomplete dates will be imputed by the methods specified in the attachment (Section 4.1).

Baseline ECOG score and BRCA1 or BRCA2 mutation status will be summarized using frequency counts. A frequency tabulation of the number of subjects with and the different types of previous cancer surgery, radiotherapy, or systemic therapy will be given. A listing of all pre-planned surgeries will be generated. A summary of medical and surgical history will be presented per system (none, history, currently active). Baseline ECG and LVEF (Left Ventricular Ejection Fraction) will be summarized.

#### **2.2.4. Discontinuation Information**

The number of subjects enrolled per center and subject disposition will be summarized by randomization arm. Subject disposition includes the number of subjects in each of the following categories:

- Randomized
  - Not Treated (subjects who are randomized but not treated with trabectedin or DOXIL)
  - Treated (subjects who are treated with trabectedin or DOXIL)

An additional table will be created for all treated subjects, displaying for each treatment group the reason for treatment discontinuation by cycle.

A separate listing will be provided for subjects not treated.

Reasons for treatment termination will be collected on the CRF and will be summarized for all randomized subjects with the following categories:

- Overt progression of neoplastic disease
- Subject Choice
- Adverse Event

YONDELIS®: Statistical Analysis Plan Study ET743-OVC-3006

- Death
- Subject completed 2 cycles of treatment after confirmed CR
- Other
- Lost to follow-up

The discontinuation reason due to an adverse event is further classified into drug-related and non-drug-related adverse events.

### **2.2.5. Extent of Exposure**

#### **Cycle duration:**

Cycle duration (weeks) is defined as:

$[(\text{The earliest dosing date of trabectedin or DOXIL in the next cycle}) - (\text{the earliest dosing date of trabectedin or DOXIL in the current cycle})] / 7$

For the final cycle, cycle duration is equal to the pre-planned duration, ie, 3 weeks for the trabectedin + DOXIL arm and 4 weeks for the DOXIL arm.

#### **Treatment duration:**

The treatment duration (weeks) is defined as:

$[(\text{The last cycle end date}) - (\text{the first cycle start date}) + 1] / 7$

#### **Cumulative dose:**

Cumulative will be calculated for DOXIL and trabectedin separately.

The cumulative dose during the treatment is defined as:

Sum of dose infused across at each cycle (mg) / the Body Surface Area (m^2) at each cycle

#### **Dose intensity:**

Dose intensity will be calculated for DOXIL and trabectedin separately.

Dose intensity during the treatment is defined as:

Cumulative dose/treatment duration.

The dose intensity is expressed in mg/m^2/per 3 weeks for the trabectedin + DOXIL arm, and in mg/m^2/per 4 weeks for the DOXIL arm.

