**Treatment Options – Amendment 6:**

For subjects assigned to Arm A (trabectedin+DOXIL), treatment with trabectedin should be immediately discontinued. All study subjects (Arm A or Arm B) currently on study who, in the opinion of the investigator, are deriving clinical benefit may continue treatment with single-agent DOXIL as per the local standard of care. Treatment for these subjects may continue as long as the subjects comply with protocol-specified prohibitions and restrictions for treatment (Section 4.3) and as long as they experience clinical benefit in the opinion of the investigator. DOXIL will be provided by the JR&D as needed until post-trial access to DOXIL is available or until disease progression, whichever occurs first.

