For subjects in Treatment Arm A who are required to discontinue treatment with either trabectedin or DOXIL, treatment with the other agent may continue if the subject is benefiting from therapy. Subjects in Treatment Arm A who receive 2 dose reductions of trabectedin because of toxicity or can no longer receive dexamethasone or use a central line, may receive DOXIL as a single agent. For subjects in Treatment Arm A who receive 2 dose reductions of DOXIL or can no longer receive DOXIL because of cardiac or other toxicity, may receive trabectedin as a single agent. If the dose has not been previously reduced for related toxicity, the dose of the continued single-agent drug may be increased as monotherapy to 1.3 mg/m^2 for trabectedin every 3 weeks or 35 mg/m^2 for DOXIL every 3 weeks. The new dose will be subject to the same rules for adjustment as described above in this section. If DOXIL is discontinued due to cardiac toxicity, then refer to [Table 5](#) for treatment guidelines for trabectedin monotherapy.

Any significant decrease in LVEF (defined as absolute decrease ≥15%, or less than LLN and absolute decrease ≥5%) should be captured as an adverse event regardless of assessed clinical significance or action taken. The supplemental cardiac adverse events form should also be completed for these adverse events.

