## 2. ANALYSES PLANNED

### 2.1. General Analysis Definitions

#### 2.1.1. Definition of Cycle, Treatment Phase, Baseline

**Cycle:** The duration of cycles may not consistently be as the planned 21 days in the trabectedin + DOXIL Arm or 28 days in the DOXIL Arm, it will depend on the earliest date of the DOXIL/trabectedin doses given in the next cycle. If a subject experiences toxicity at the planned start of a cycle that leads to a delay in DOXIL/trabectedin administration, this new cycle will be delayed, and the previous cycle will be prolonged (without additional DOXIL or trabectedin treatment).

The start of the cycle is the date of the first administration of DOXIL or trabectedin in a cycle. The end of a cycle is the day before the first infusion of the immediate subsequent cycle recorded on the case report form (CRF).

The last cycle ends 3 weeks after the start of this cycle for the trabectedin + DOXIL Arm, and 4 weeks for the DOXIL Arm.

The assessments performed during the 'End-of-treatment visit' will be included in the last treated cycle for analysis.

All lab samples taken after the last treatment and up to 30 days after the last DOXIL/trabectedin infusion will be captured in the last cycle.

**End-of-treatment phase:** The end of the treatment phase is the date the last cycle ends, i.e., 3 weeks after the first trabectedin or DOXIL dosing in the last cycle for Arm A, or 4 weeks after the dose of DOXIL in the last cycle for Arm B.

YONDELIS®: Statistical Analysis Plan Study ET743-OVC-3006

**Follow-up phase:** Following termination of DOXIL/trabectedin treatment, subjects are followed every 8 weeks for survival for the first 2 years after randomization and every 3 months thereafter until death or the clinical cut-off date defined at the time when 514 deaths are observed, whichever is sooner. If disease progression has not occurred at treatment termination, then disease assessment should continue every 8 weeks until there is evidence of disease progression or death, or until the clinical data cut-off date, or until the start of first subsequent therapy for ovarian cancer, whichever is earlier. Disease assessment will also be done if necessary to confirm response or document disease progression.

**Relative day:** Assessments will be presented chronologically by cycle day or study day, which are defined in the following:

Cycle day = assessment date - date of first DOXIL or trabectedin infusion for the cycle + 1

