**Relative Dose intensity:**

Relative dose intensity will be calculated for DOXIL and trabectedin separately.

Relative dose intensity is the dose intensity divided by the planned dose intensity. The planned dose intensity is 1.1 mg/m^2/per 3 weeks for trabectedin in the trabectedin + DOXIL arm, 30mg/m^2/per 3 weeks for DOXIL in the trabectedin + DOXIL arm, and 50mg/m^2/per 4 weeks for DOXIL in the DOXIL arm.

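### Dose intensity is calculated per drug but over one regimen-wide duration, so in Arm A a drug stopped on its own scores as under-delivered, while in Arm B the same number of full DOXIL cycles scores about 100%

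*SAP*

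**What the plan says.** SAP section 2.2.5 states that "Dose intensity will be calculated for DOXIL and trabectedin separately" and gives the formula as "Cumulative dose/treatment duration". Only one duration is available for the denominator: "The treatment duration (weeks) is defined as" the span from the start of the first cycle to the end of the last, plus one day, divided by 7. It is a single value per subject.

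In SAP section 2.1.1 the cycle is a regimen unit: "The start of the cycle is the date of the first administration of DOXIL or trabectedin in a cycle". The Arm A treatment phase ends "3 weeks after the first trabectedin or DOXIL dosing in the last cycle for Arm A".

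For the relative measure, "Relative dose intensity is the dose intensity divided by the planned dose intensity". The references are fixed: 1.1 (trabectedin) and 30 (DOXIL) mg/m² per 3 weeks in Arm A, and 50 mg/m² per 4 weeks in Arm B.

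Protocol section 6.2.2, in the text after Table 5, says that when an Arm A subject has to stop one drug, "treatment with the other agent may continue if the subject is benefiting from therapy". If the remaining drug has not been reduced for related toxicity, its dose may be raised to 1.3 mg/m² (trabectedin) or 35 mg/m² (DOXIL) every 3 weeks. Under Amendment 6 (Protocol section 6), in Arm A "treatment with trabectedin should be immediately discontinued", and DOXIL may continue.

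**The concern.** The numerator belongs to one drug and the denominator to the regimen. Once an Arm A subject is on a single drug, the stopped drug keeps accruing time at zero dose. In Arm B, stopping DOXIL ends the last cycle and so stops the clock. For DOXIL, the drug common to both arms, the plan in effect uses regimen time in Arm A and on-drug time in Arm B, without saying so.

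A reader who compares DOXIL relative dose intensity between arms will take a lower Arm A figure as more reduction or delay. Part of it may only be earlier stopping of one component. The other planned tables do not clearly separate the two. SAP 2.2.5 gives one cycle count per subject, and the termination reasons in SAP 2.2.4 are not broken down by drug. Because the monitoring committee cited higher Arm A toxicity when it recommended stopping, readers are likely to use the exposure tables to interpret that toxicity.

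**Working it through.** **Inputs from the documents.** Planned doses 30 and 1.1 mg/m² per 3 weeks (Arm A) and 50 mg/m² per 4 weeks (Arm B); last cycle counted as 3 or 4 weeks; permitted single-agent doses 1.3 and 35 mg/m².

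**Assumed.** The cycle counts k and n, with every dose full and on time.

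**Formula.** RDI = [sum of doses in mg/m² ÷ duration in weeks × planned cycle weeks] ÷ planned dose intensity.

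**1. The plan's own figures.** Six full, on-time cycles:
- Arm A DOXIL: 6×30 ÷ 18 × 3 = 30
- Arm A trabectedin: 6×1.1 ÷ 18 × 3 = 1.1
- Arm B DOXIL: 6×50 ÷ 24 × 4 = 50

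All three reproduce the planned values, so RDI is 100%. If the plus-one term adds a day to a last cycle already ending 21 or 28 days after its start, they become 29.76, 1.091 and 49.70 (99.2%, 99.2%, 99.4%).

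**2. One Arm A drug stopped after k of n cycles, the other continued.** With planned dose D: RDI = [kD ÷ 3n × 3] ÷ D = k/n.

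| k of n | Arm A, stopped drug | Arm B, DOXIL stopped after k cycles |
|---|---|---|
| 2 of 8 | 25% | 100% |
| 4 of 10 | 40% | 100% |
| 4 of 8 | 50% | 100% |
| 6 of 8 | 75% | 100% |

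With the extra day, the 4-of-10 case is 84/211 = 39.8% against 112/113 = 99.1%. Across the table, Arm B runs from 98.2% to 99.4%.

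**3. Per-drug duration.** If each drug's own time is the denominator, RDI = [kD ÷ 3k × 3] ÷ D = 100% for every k (97.7% to 99.2% with the extra day, k = 2 to 6). This matches Arm B.

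**4. The continued drug.** At an unchanged dose it scores 100%. At the permitted single-agent dose it runs at 1.3/1.1 = 118% or 35/30 = 117% in those cycles. Over 4 combination and 6 single-agent cycles:
- trabectedin: (4×1.1 + 6×1.3) ÷ (10×1.1) = 12.2/11 = 111%
- DOXIL: (4×30 + 6×35) ÷ (10×30) = 330/300 = 110%

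**5. Arm level.** If a fraction p of Arm A subjects stop a given drug at k of n cycles and the rest score 100%, that drug's mean falls by p × (1 − k/n). With k/n = 1/2, p = 10% to 30% gives 5 to 15 points. These p values are assumptions, not figures from the documents. The nearest documented figure is the 6% with an LVEF decrease in the earlier phase 3 study's combination arm (Protocol 1.2.2). It gives 6% × 50 = 3 points for the cardiac route, if every such case led to a single-drug stop halfway through.

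**6. Amendment 6.** It is dated 9 January 2018, and data collection ends by 18 January 2018. With 3-week cycles, at most one DOXIL-only infusion per subject falls in those 9 days. If one were recorded after 4 combination cycles, trabectedin RDI would be 4/5 = 80%.

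**The case against.** Regimen time is a coherent denominator. A subject given 4 DOXIL doses in 10 cycles did receive 40% of the DOXIL planned over that time. A per-drug duration has the opposite weakness: one trabectedin cycle out of ten would score 100% and hide the early stop. The Arm B comparison is also not the same event, because stopping the only drug ends the regimen, and an Arm A subject who stops both drugs together scores 100% too. Per-drug cumulative dose is unaffected. Cycle delays, dose reductions, and adverse events leading to skipped doses or withdrawal have their own tables. No test uses dose intensity.

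All of that stands. It does not remove the mismatch for the shared drug, and the SAP neither says that the measure is regimen-based nor gives a rule for single-agent cycles.

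Stronger readings go beyond the documents:
- A reader might infer that the fixed combination dose also makes Arm A look under-dosed. It enters only relative dose intensity, and it pushes the continued drug up, not down.
- A reader might infer that Amendment 6 pulls trabectedin figures down widely. The 9-day window leaves little room, and DOXIL continued under local standard of care carries only serious adverse event reporting, so it may not be recorded as study dosing at all.
- A cardiac DOXIL stop looks like the natural example, but the protocol conflicts with itself there. Section 6.1 stops DOXIL when LVEF has fallen and is below the lower limit of normal, and continues trabectedin at the same dose if Table 1 is met. Table 1 requires LVEF at or above that limit, and section 6.1 caps delay at 3 weeks. Table 5 leaves trabectedin unchanged at a first occurrence, while the text after it allows a single-agent increase but refers cardiac stops back to Table 5. The values above 100% therefore should not be attached to cardiac stops.

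**Conclusion.** The point holds as a matter of definition and is a cheap improvement. For a full-dose, on-time subject, the stopped Arm A drug scores k/n, against about 100% for an Arm B subject with the same number of DOXIL cycles. The continued drug can exceed 100% only where the optional single-agent increase is used.

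The individual figures assume no reduction or delay, and cycle counts chosen for illustration. The arm-level shift cannot be determined, because the documents do not say how often one drug is stopped alone; 5 to 15 points is what assumed frequencies produce, not an estimate. A reader might also infer consequences for the trial's conclusions. There are none for overall survival, type I error or power; the effect is confined to descriptive exposure tables.

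**What to change.** In SAP section 2.2.5:

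- Define a duration for each drug, from its first dose to the planned end of the last cycle in which it was given. Report that drug's dose intensity and relative dose intensity on it, beside the regimen-duration figure, with each labelled.
- Report single-agent cycles in a separate row.
- Tabulate the Arm A subjects who stopped one drug and continued the other, by drug and reason, with Amendment 6 as its own reason.

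Before a reference for single-agent cycles is set, Protocol section 6.1 (with Table 1), Table 5 and the text after Table 5 must be reconciled on trabectedin after a cardiac DOXIL stop.

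The cost is SAP wording, a few lines of code on dosing data already collected, and one or two extra exposure rows. The two Arm A drugs may show different durations. The per-drug figure does not reflect early stopping, which is why the regimen-based figure and the count should stay beside it.

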**Relative Dose intensity:**

Relative dose intensity will be calculated for DOXIL and trabectedin separately.

Relative dose intensity is the dose intensity divided by the planned dose intensity. The planned dose intensity is 1.1 mg/m^2/per 3 weeks for trabectedin in the trabectedin + DOXIL arm, 30mg/m^2/per 3 weeks for DOXIL in the trabectedin + DOXIL arm, and 50mg/m^2/per 4 weeks for DOXIL in the DOXIL arm.

**Number of Cycles:**

For each subject, total number of cycles received will be calculated.

Descriptive statistics of treatment duration, cumulative dose, dose intensity, relative dose intensity, and the number of cycles received will be presented.

**Cycle Delay, Dose Reduction:**

The number of subjects with a cycle delay will be summarized by the number of delays. The number of subjects with a dose reduction will be summarized by the number of reductions. The reasons for cycle delay or dose reduction are further classified into drug-related adverse event (AE), non drug-related AE, or other reason. Only delays of at least 5 days will be used for the summary table. All delays will be provided on the listing.

A listing will be generated containing the data of those trabectedin and DOXIL infusions that have been interrupted along with the reason.

Dosing information of dexamethasone will be listed.

**2.2.6. Protocol Deviations**

Protocol Deviations will be summarized for all randomized subjects.

A summary table with the number of inclusion/exclusion violators will be presented per criterion. These subjects will be listed with the criteria that are not met.

Important protocol deviations will be documented during the trial execution based on pre-defined criteria. The detailed criteria will be documented in the data management plan and will be agreed to by the Janssen Research & Development, LLC (Janssen R&D) project physician. The classification of such protocol deviations will also be reviewed by the Janssen R&D project physician and finalized prior to the database lock. Once identified and recorded according to the rules, deviations will not be removed from the database.

YONDELIS®: Statistical Analysis Plan Study ET743-OVC-3006

Summary will be presented including the following categories:

- Selection criteria not met
- Subject not withdrawn as per protocol
- Treatment deviation
- Excluded concomitant medication
- Efficacy assessment deviation
- Other

### **2.2.7. Concomitant Medications**

Concomitant therapies will be categorized per coded term. The number of subjects receiving each type of therapy during the treatment phase will be tabulated in 2 separate tables: a frequency tabulation of the different therapies that started pre-trial, and a frequency tabulation of the different therapies that started during the trial. The accompanying listing will contain all concomitant therapies.

### **2.2.8. Efficacy**

#### **2.2.8.1. Analysis Specifications**

##### **2.2.8.1.1 Level of Significance**

For the primary endpoint OS, the overall (two-sided) significance level is 0.05. This 0.05 will be spread over 2 analyses by an O'Brien-Fleming boundaries as implemented by Lan-DeMets alpha spending function. The significance of efficacy will be claimed if the p-value is less than or equal to the significance level as calculated based on the above specified alpha spending function and the observed number of events.

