## **2.2. Methods of Analysis**

Final efficacy and safety analysis for the CSR will be using clinical cut-off date of January 18, 2018.

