### **2.2.1. Statistical Hypotheses for Trial Objectives**

Overall Survival (OS) will be compared between treatment arms using an unstratified one-sided log-rank test. The trabectedin + DOXIL combination therapy will be declared better than DOXIL monotherapy if the OS is better with a p-value less than or equal to the significance level as specified by the alpha spending function. The overall 2-tailed significance level of 0.05 will be spread over 1 interim and 1 final OS analyses, when approximately 308 and 514 events on OS (death) are seen.

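### The SAP does not say what significance level applies to the one remaining OS analysis: 0.05, or about 0.002 to 0.007 from a two-look rule that is no longer followed

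*SAP*

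**What the plan says.** Two statements define the analysis that will be done. SAP 2.2: "Final efficacy and safety analysis for the CSR will be using clinical cut-off date of January 18, 2018". SAP 2.2.2.2, after reporting the futility result: "The planned interim analysis will not be performed". Together they leave one efficacy look at OS, set by date and not by event count.

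Other current text still describes the abandoned design:

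- SAP 2.2.1: the two-tailed 0.05 "will be spread over 1 interim and 1 final OS analyses, when approximately 308 and 514 events on OS (death) are seen".
- SAP 2.2.8.1.1: "For the primary endpoint OS, the overall (two-sided) significance level is 0.05", and then "This 0.05 will be spread over 2 analyses by an O'Brien-Fleming boundaries as implemented by Lan-DeMets alpha spending function". Success is judged against the "significance level as calculated based on the above specified alpha spending function and the observed number of events".
- SAP 2.2.2.2: the table keeps HR bounds of 0.74 at 308 deaths and 0.84 at 514.
- SAP 2.1.1: survival follow-up runs to death or "the clinical cut-off date defined at the time when 514 deaths are observed".

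The sidedness also differs. SAP 2.2.1 specifies a one-sided log-rank test; SAP 2.2.8.2 and protocol 11.3 specify a two-sided one.

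The SAP was edited after the stop. Hierarchical testing, the OS subgroup analyses and the patient-reported outcome analyses are each marked as not to be performed. The OS success rule carries no such note, and 2.2.8.2 keeps the log-rank comparison as the primary analysis.

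**The concern.** A spending function needs two inputs: the deaths observed and the total that counts as full information. SAP 2.2.8.1.1 supplies the first. For the second, the only figure anywhere is 514. With the two-analysis wording still in force, the literal reading places the January 2018 look at D/514, as if it were an early interim. Most of the 0.05 would then be held back for a later look that will never take place. The other reading treats this as the final look, at which all unspent alpha is available. The SAP states neither.

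At stake is whether the primary result can be classified without a decision made after the data are seen. Take a hypothetical HR of 0.75 at 270 deaths. The two-sided p is 0.018 and the 95% CI is about 0.59 to 0.95, so the CI requested in SAP 2.2.8.2 excludes 1. The literal level at 270 deaths is 0.0040, so 2.2.8.1.1 would call the same result not significant.

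The sidedness conflict adds to this. A one-sided p set against half the two-sided level is the same test. Set against the whole of it, it doubles the error allowed in favour of the combination.

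**Working it through.** **Inputs.** Two-sided alpha 0.05, Lan-DeMets O'Brien-Fleming spending, looks at 308 and 514 deaths (SAP 2.2.1, 2.2.2.2, 2.2.8.1.1). 1:1 allocation, HR 0.78, 80% power (SAP 1.3). About 232 deaths, 45% of 514, and HR 0.962 at the second futility look, whose data ran to 20 September 2017 (SAP 1.2, 2.2.2.1).

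**Assumption.** The death count at 18 January 2018 is not given. I use 232 to 300. The planned pace between the two looks is (514 − 308)/(64 − 43) = 9.8 deaths a month; four months of that adds about 39 to 232, giving roughly 270.

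**Formulas.** The two-sided level at information fraction t is 4 × [1 − Φ(2.2414/√t)], that is, twice a one-sided 0.025 spend. Critical HR = exp(−2z/√D). Power at HR 0.78 = Φ(0.2485 × √D/2 − z).

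**Reproducing the plan.**

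- Events (Freedman): (1.960 + 0.842)² × (1.78/0.22)² = 514.
- Interim, t = 308/514 = 0.599: level 0.0076 (stated 0.008), z = 2.671, HR exp(−2 × 2.671/√308) = 0.738 (stated 0.74).
- Final, with correlation √(308/514): z = 1.981, nominal p 0.0476 (stated 0.048), HR exp(−2 × 1.981/√514) = 0.840 (stated 0.84).
- Group-sequential power at HR 0.78: 80.1%.

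The original design is internally sound.

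**The January 2018 look under the two readings.**

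| Deaths D | D/514 | Level at D/514 | Critical HR | Power at HR 0.78 | Level, terminal look | Critical HR | Power at HR 0.78 |
|---|---|---|---|---|---|---|---|
| 232 | 0.451 | 0.0017 | 0.66 | 11% | 0.05 | 0.77 | 47% |
| 257 | 0.500 | 0.0031 | 0.69 | 17% | 0.05 | 0.78 | 51% |
| 270 | 0.525 | 0.0040 | 0.70 | 20% | 0.05 | 0.79 | 53% |
| 300 | 0.584 | 0.0067 | 0.73 | 29% | 0.05 | 0.80 | 58% |

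The levels differ by a factor of 0.05/0.0017 ≈ 29 at 232 deaths and 0.05/0.0067 ≈ 7 at 300. Carrying over the planned final nominal level of 0.0476 gives critical HRs of 0.77 to 0.80, practically the same as 0.05.

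**Distance of the recorded result.** At HR 0.962 and 232 deaths, z = 0.0387 × √232/2 = 0.295, two-sided p about 0.77, approximate 95% CI 0.74 to 1.24. To reach even two-sided 0.05 at 300 deaths, the 68 later deaths would have to supply (1.96 × √300 − 0.295 × √232)/√68 = 3.57 standard errors. That is an HR of about exp(−2 × 3.57/√68) = 0.42 among those deaths alone.

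**The case against.** A reader might infer that the rule is locked to 308 and 514 deaths and is therefore simply wrong. The text does not support that. SAP 2.2.8.1.1 ties the level to the observed events, and protocol 11.8 also adjusts the alpha to the actual count. The terminal reading is also available from the text. SAP 2.2 calls the January 2018 analysis final, the table gives the final analysis a cumulative alpha of 0.050, no efficacy look was taken, and the futility looks were non-binding. This stands: the level is unspecified between two readings, not demonstrably wrong. It does not remove the gap, because an observed count without a stated total does not fix a level, and the only total given is 514.

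A reader might also count HR 0.84 as a third success threshold that would breach 5%. At 232 to 300 deaths an observed HR of 0.84 has a two-sided p of about 0.18 to 0.13, so it would be far too lenient if used. But it is an operating characteristic at the projected 514 deaths, and success is judged only on the p-value. Neither live reading of the level, applied to a two-sided test, exceeds 5%.

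The 514-death wording in SAP 2.1.1 concerns follow-up, and the protocol already pairs 514 deaths with the clinical cutoff date. That makes it leftover text to correct, not a rival analysis rule.

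The strongest objection is about consequence. With HR 0.962 recorded at about 232 deaths, no plausible January 2018 result falls between the candidate thresholds. Hierarchical testing, which depends on OS success, is cancelled. The p-value, and the HR with its 95% CI, are the same under either level. This stands and sets the severity.

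**Conclusion.** The point holds as an unresolved contradiction in the primary-endpoint rule. One efficacy look remains, the text still describes two, and the level for that look is either 0.05 or about 0.0017 to 0.0067, with nothing in the SAP to choose between them. The one-sided and two-sided statements need reconciling as well.

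The figures rest on an assumed 232 to 300 deaths at cutoff. A reader might take the analysis to have about half the planned deaths, but only the 45% at the September 2017 data cut is documented. On the same assumption, the 80% power in SAP 1.3, which belongs to 514 deaths, falls to about 47% to 58% for HR 0.78 at 0.05.

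Severity is minor to moderate. The defect lies in how the primary test is specified; the recorded result makes it very unlikely to change the trial's conclusion.

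**What to change.** In SAP 2.2.1, 2.2.2.2 and 2.2.8.1.1, state that:

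- the analysis at the 18 January 2018 cutoff is the sole efficacy analysis of OS;
- the two futility looks were non-binding and spent no alpha;
- the log-rank test is two-sided at 0.05, reported with a 95% CI, and the one-sided wording in 2.2.1 is removed;
- the looks at 308 and 514 deaths and their HR bounds of 0.74 and 0.84 describe the original design and no longer apply.

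In SAP 2.1.1, replace the 514-death definition of the cutoff with 18 January 2018. In SAP 1.3, note that the 80% power refers to 514 deaths and does not apply at the cutoff. Report the actual number of deaths with the result, as 2.2.8.2 already requires.

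If the sponsor would rather treat the OS p-value as descriptive, because efficacy had already been judged lacking, that is defensible, but it also has to be stated.

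The cost is wording only: no new data and no new analysis. The one uncomfortable consequence is saying openly that power for the design effect at this cutoff is roughly half.
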